### 1. Aim of the study

The aim of the present multi-centre, cross-sectional study is to determine the prevalence and incidence of mucositis and peri-implantitis. Furthermore, with the help of a cytokine analysis of peri-implant swab samples and of blood lymphocytes or monocytes on titanium platelets and particles *in vitro*, the tolerance of titanium in relation to the clinical conditions will be examined. In total, a maximum of 200 patients will be examined at 10 centers over a period of 6 months using clinical, genetic and microbiological parameters.

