### 3. Inclusion criteria for patients

- Presence of at least one helical dental implant made of cp-Ti with an insertion date after April 1st, 2001
- No other titanium implants in the body

- Regular participation in a recall

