##### 4.2 Clinical investigation parameters

For patients with multiple implants, a maximum of two implants are examined, the most clinically noticeable and one normal implant. All measurements are carried out by a previously calibrated person using a PCP 12 periodontal probe (Hu-Friedy kal, Germany).

The following clinical parameters are determined:

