#### 4.4 blood test

A blood sample (fresh heparinized blood) is taken from each patient, with which a lymphocyte activation test is carried out in vitro. For this purpose, the samples are sent overnight to the [name] / LMU Munich. There, lymphocytes and monocytes are isolated from the samples and incubated in vitro with titanium particles and on titanium plates from Astra, Camlog, Dentsply, Nobel Biocare and Straumann. After several days of culture, the release of inflammatory cytokines is measured (IL-1, IL-6, IL-8, interferon  $\gamma$ , TNF $\alpha$ , TNF $\beta$ , MMPs, etc.). Furthermore, a DNA bank for further polymorphism studies is created from a small additional sample and the CRP, beta crosslaps and HbA1c values are measured from the serum sample obtained.

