#### 4.5 IL-1 polymorphism analysis

With the help of a brush (GenoType® PST® plus, Hain Lifescience GmbH, Nehren), a smear is also taken in the peri-implant area. The brushes are then placed in a test tube and examined in the laboratory for an IL-1 polymorphism (Bioscientia GmbH, Ingelheim).

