#### 4.6 Microbiological test parameters

A microbiological examination is carried out on all patients. For this purpose, the qualitative and quantitative presence of *Aggregatibacter actenomycetemcomitans* (Aa), *Porphyromonas gingivalis* (Pg), *Prevotella intermedia* (Pi), *Tannerella forsythia* (Tf), *Treponema denticola* is determined with a marker germ analysis (micro-IDent® plus, Hain Lifescience GmbH, Nehren) (Td), *Peptostreptococcus micros* (Pm), *Fusobacterium nucleatum* (Fn), *Campylobacter rectus* (Cr), *Eubacterium nodatum* (En), *Eikenella corrodens* (Ec) and *Capnocytophaga* sp. (C.sp.) examined. For this purpose, after the examination area has dried, a sterile paper tip is inserted to the bottom of the respective peri-implant pocket and left there for about 20 seconds. These are then placed in a test tube and examined in a laboratory (Bioscientia GmbH, Ingelheim).

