#### 4.7. Quantitative determination of the protein aMMP-8

Furthermore, a quantitative determination of the tissue-degrading protein aMMP-8 is carried out in all patients (Bioscientia GmbH, Ingelheim).

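### Does the aim promise a cytokine analysis of peri-implant swabs that no procedure in section 4 delivers?

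*Protocol*

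**What the plan says.** Section 1 names prevalence and incidence of mucositis and peri-implantitis as the aim. It then adds that titanium tolerance will be studied "with the help of a cytokine analysis of peri-implant swab samples and of blood lymphocytes or monocytes on titanium platelets and particles". Two kinds of material are therefore named for the cytokine work: local swabs and blood cells. The same section sums up the examination as "using clinical, genetic and microbiological parameters".

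The laboratory procedures are in 4.4 to 4.7:

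- **4.4**, on cultured blood cells: "After several days of culture, the release of inflammatory cytokines is measured". The list of analytes that follows includes MMPs.
- **4.5**, on a brush smear from around the implant: "The brushes are then placed in a test tube and examined in the laboratory for an IL-1 polymorphism".
- **4.6**, for the bacterial markers: "a sterile paper tip is inserted to the bottom of the respective peri-implant pocket and left there for about 20 seconds".
- **4.7**, in full apart from the laboratory's name: "a quantitative determination of the tissue-degrading protein aMMP-8 is carried out in all patients".

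Two further statements bear on which implant a local sample would come from. Section 3 requires only "Presence of at least one helical dental implant made of cp-Ti", so patients with a single implant are eligible. Section 4.2 says: "For patients with multiple implants, a maximum of two implants are examined, the most clinically noticeable and one normal implant". Section 5 then relates peri-implant inflammation to genetic, immunological and microbial factors.

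**The concern.** A reader who takes the aim at its word and looks for the matching procedure does not find one. Only 4.4 states a cytokine readout, and its specimen is blood. The two procedures that name a peri-implant specimen yield a genotype and a bacterial profile. The genotype is fixed for the patient, so it cannot describe a local response or differ between a noticeable and a normal implant. Section 4.7 could fill the place, but it is the only one of the four sections that does not say what is sampled.

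Two things would be at stake. In a cross-sectional study a specimen not collected at the examination cannot be obtained afterwards. If aMMP-8 were not measured locally, the swab route to the titanium-tolerance aim would produce no data. If it is measured locally, a patient with two examined implants could have a value whose source is unclear, and section 5 would have difficulty relating it to the inflamed or the normal site. Specimen and assay are also matters for a protocol, so a separate analysis plan would not be expected to supply them.

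**Working it through.** The protocol gives no figure on this point, so the check sets aim and procedures side by side.

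**Step 1. Specimen and analyte in each laboratory section.**

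| Section | Specimen stated | What is measured | Laboratory named |
|---|---|---|---|
| 4.4 | Heparinized blood | Cytokine release after culture; also a DNA bank, CRP, beta crosslaps and HbA1c | Munich, for the cell work |
| 4.5 | Brush smear, peri-implant | IL-1 polymorphism | Commercial laboratory |
| 4.6 | Paper tip, peri-implant pocket | 11 bacteria | Same commercial laboratory |
| 4.7 | None stated | aMMP-8 | Same commercial laboratory |

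Sections naming a peri-implant specimen: 2 of 4. Of these, sections stating a cytokine assay: 0 of 2. Over all four, sections stating a cytokine assay on a peri-implant specimen: 0 of 4. The mismatch in wording is real.

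**Step 2. Is a measurement missing, or only its description?** Three features of the text bear on this.

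- Section 4.4 places MMPs in its list of inflammatory cytokines. In this protocol's vocabulary, an assay of aMMP-8 falls under cytokine analysis.
- Section 4.7 comes directly after the pocket sampling in 4.6 and opens as a continuation of it.
- Section 4.7 names the laboratory that receives the brush and the paper tip, whereas the blood for cell culture goes to Munich.

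All three favour a local aMMP-8 measurement. None proves it: 4.4 does not say where its serum values are determined, so the laboratory's name alone does not exclude blood.

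**Step 3. Does the summary phrase in section 1 count against this?** The phrase "using clinical, genetic and microbiological parameters" mentions nothing immunological. But it also leaves out the blood-cell cytokine assay, which 4.4 plainly includes. Its silence therefore says nothing about 4.7.

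**Step 4. Which implant?** In a patient with one implant there is only one possible source. In a patient with two, 4.6 describes sampling the pocket with the word *respective*, which can be read as each examined implant. If 4.7 shares that sampling, each implant has its own value. The protocol does not say that implant position goes unrecorded.

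**Step 5. Can the size be calculated?** Let p be the share of patients with two examined implants, and take the maximum of 200 patients.

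- One unlabelled aMMP-8 value per patient: values of unclear source = 200 × p, so from 200 × 0 = 0 to 200 × 1 = 200.
- One labelled value per examined implant: 0, whatever p is.

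The protocol states neither p nor the number of values per patient. The range runs from none to all, so it is no evidence of harm.

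**Step 6. What would an edit alter?** On the likelier reading, 4.7 would gain the name of a specimen and an implant, and section 1 would name aMMP-8. No measurement is added, no rule or figure that would give a wrong result is corrected, and the results on prevalence, on blood cells and in section 5 stay the same.

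**The case for a change.** The strongest case for a change is that 4.7 stands out. Its three neighbours each name their specimen, and staff at up to 10 centers must sample alike in a single examination. The wording would be cheap to add. Even if aMMP-8 is the local marker, the aim speaks of cytokine analysis in general where one protein is measured. And if 4.7 were in fact a blood measurement, one part of a stated aim would have no procedure behind it, which later analysis could not repair.

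Part of this stands. The aim and section 4 do not match in words, the identification of aMMP-8 as the local marker is an inference, and the aim's wording is broader than a single analyte. The consequences do not follow so readily. The protocol's own terms, the order of its sections and the laboratory it names all point one way, so the branch with no swab data is the less likely one. That the protocol does not mention implant labelling does not show that values cannot be matched to implants; such labelling may sit in sampling forms or laboratory instructions that are not part of this document. Even in the unfavourable branch the loss would be confined. The tolerance claim would have to rest on the in vitro blood-cell response, and section 5 could still take immunological factors from 4.4.

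**Conclusion.** The observation about the wording is correct, but it calls for no change to the plan. It is a gap in description that those running and analysing the study can fill sensibly: aMMP-8 is most naturally read as the local inflammatory marker, related to the implant it was taken from.

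Its reach is one of two routes to a secondary aim. The prevalence aim and the blood-cell assay in 4.4 are untouched, and the count of 0 in 4 sections measures explicit wording, not missing data. No number of affected patients can be given, because the document states neither the share with two examined implants nor the number of aMMP-8 values per patient.

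The conclusion rests on two assumptions: that 4.7 uses a peri-implant sample, which the text supports but does not state, and that samples are labelled by implant in the ordinary way. If the first proved false, the report would have to confine its titanium-tolerance statement to the blood-cell findings; the other results would stand.

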### 2. Material and methods

200 patients will be enrolled in the study at a maximum of 10 centers (20 patients per center) that have been presented for a routine check-up. The centers are 3 university clinics, a hospital and 6 private practices:

- Clinic for Periodontology at the University of Bern
- Polyclinic for Dental Surgery and admission to Heinrich Heine University Düsseldorf
- Clinic for Maxillofacial Surgery at the Georg-August University in Göttingen
- Clinic for maxillofacial surgery at the Red Cross Hospital Kassel
- Private dental practice [name] / Filderstadt
- Private dental practice [name] / Memmingen
- Private dental practice [name]. [name] / Vienna, Austria
- Private dental practice [name] [name] / Wetzlar
- Private dental practice [name] / Cham
- Private dental practice PD [name] / Bitburg

Titanium implants had been placed in all of the test subjects in the individual centers within the last 10 years. After the implantation, they were included in a regular recall system. All test subjects are informed in detail about the course of the study both verbally and in writing and give their written consent. At any point in time, the patient has the option of leaving the examination. The study protocol is checked by the ethics committees of the medical faculties of Heinrich Heine University in Düsseldorf, Georg-August University in Göttingen, Ludwig Maximilian University in Munich and the University of Bern.

### 3. Inclusion criteria for patients

- Presence of at least one helical dental implant made of cp-Ti with an insertion date after April 1st, 2001
- No other titanium implants in the body

- Regular participation in a recall

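### Implant loss and earlier peri-implantitis treatment are not recorded, so incidence and ever-affected proportions would be too low and some past cases would count as unaffected in the titanium-tolerance correlation

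*Protocol*

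**What the plan says.** Section 1 sets two aims. One is epidemiological: the "cross-sectional study is to determine the prevalence and incidence of mucositis and peri-implantitis". The other is biological: "the tolerance of titanium in relation to the clinical conditions will be examined".

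Section 2 sets the look-back: "Titanium implants had been placed in all of the test subjects in the individual centers within the last 10 years". Section 3 admits patients on "Presence of at least one helical dental implant made of cp-Ti", inserted after 1 April 2001, and on "Regular participation in a recall". Neither section says anything about implants that have since been lost or removed.

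Section 4.1 lists the history to be taken: internal diseases, diabetes, two drug groups, allergies and smoking. Section 4.2 limits the examination: "a maximum of two implants are examined, the most clinically noticeable and one normal implant". Plaque, bleeding and probing depth are measured around those implants. Section 4.3 compares the current X-ray with the one taken when the superstructure was fitted. Section 5 derives prevalence from the clinical and radiological findings, and then correlates peri-implant inflammation with genetic, immunological and microbial factors.

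**The concern.** Implants may have been in place for up to about 10 years, long enough for some to have been lost to the disease under study. Followed as written, the plan deals with such patients in one of three ways:

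- A patient with no qualifying implant left cannot enter.
- A patient with another implant, or a replacement, that is diseased enters and is counted as a case.
- A patient with another implant, or a replacement, that is healthy enters and is classified as unaffected.

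The first and third routes lose an event that has already happened. This affects two results. An incidence, or a proportion ever affected since placement, would be too low. In the correlation with cytokine response, the unaffected group would include some people who did have peri-implantitis. If poor tolerance of titanium contributes to loss, these patients resemble the affected group and pull the contrast towards zero. An analysis plan could not repair this, because the data item would not exist.

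**Working it through.** **What the plan lets us reproduce.** The only figure is enrolment: 10 centres × 20 patients = 200, which agrees. No expected prevalence, loss rate or precision target is given, so everything below rests on assumed inputs.

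**Which quantity is affected.** Prevalence at the visit refers to implants present at the visit. A lost implant is not a prevalent case, so the shortfall against current prevalence among patients with implants in place is 0. The shortfall arises only against the ever-affected proportion, and against any incidence built from it.

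**Illustration 1.** Take 100 recall patients. Assume 20 were ever affected, that a fraction f of these lost the affected implant (10 to 25%), and that all other affected patients are still diseased at the visit.

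- Loss patients ineligible: recorded proportion = (20 − 20f)/(100 − 20f).
  - f = 0.10: 18/98 = 18.4%, shortfall 1.6 points.
  - f = 0.25: 15/95 = 15.8%, shortfall 4.2 points.
- All loss patients enter on a healthy implant (upper bound): recorded proportion = (20 − 20f)/100.
  - f = 0.10: 18%, shortfall 2 points.
  - f = 0.25: 15%, shortfall 5 points.
- Share of the unaffected group that is really past disease, in the upper-bound case:
  - f = 0.10: 2/(80 + 2) = 2.4%.
  - f = 0.25: 5/(80 + 5) = 5.9%.
  - Among 200 enrolled, this is 4 of 164 or 10 of 170 patients.
- Sampling error for comparison: 1.96 × √(0.2 × 0.8/200) = 5.5 points, ignoring clustering by centre.

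**Illustration 2, wider range.** Let p be the prevalence among patients with implants in place, and L the share of implanted recall patients who lost implants to peri-implantitis. Ever-affected = L + (1 − L)p. If loss patients are excluded, the observed value is p and the shortfall is L(1 − p). If all are scored healthy, the observed value is (1 − L)p and the shortfall is L, that is 1 to 10 points over the range below.

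| p | Shortfall if excluded, L = 1% | L = 2% | L = 5% | L = 10% | 95% half-width, n = 200 |
|---|---|---|---|---|---|
| 10% | 0.9 | 1.8 | 4.5 | 9.0 | 4.2 |
| 20% | 0.8 | 1.6 | 4.0 | 8.0 | 5.5 |
| 30% | 0.7 | 1.4 | 3.5 | 7.0 | 6.4 |
| 40% | 0.6 | 1.2 | 3.0 | 6.0 | 6.8 |

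(All shortfalls and half-widths are in percentage points.) At L of 1 to 2% the shortfall lies well inside sampling error. At 5% it passes the half-width only at p = 10%. At 10% it passes it except at p = 40%.

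**Effect on the correlation.** Let Δ be the true mean difference in cytokine response between ever-affected and never-affected patients. Suppose past-loss patients respond like other affected patients and make up a share c of the unaffected group. The observed difference is then Δ(1 − c). With c between 2.4 and 5.9%, about 2 to 6% of the difference is lost. It would be more if past-loss patients respond more strongly than other affected patients, and nothing if loss is unrelated to tolerance.

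**The case against.** The strongest reply is that a cross-sectional study measures current status, and that probing, bleeding and pocket sampling cannot be done at a lost implant. Requiring an implant in place is therefore inherent in the method. This stands. A reader might infer that the plan understates prevalence. The documents do not support that for current disease among implants in place, which is the quantity section 5 obtains from the visit findings.

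A reader might also infer that the cases most needed for the tolerance question are missing. That goes too far. Peri-implantitis on surviving implants is included, and section 4.2 deliberately picks the most conspicuous implant, so a patient with any other diseased implant is still captured. Only patients who lost every qualifying implant are absent altogether. The net direction of all selection effects is not settled either: recall-only entry and the two-implant rule also act on the observed rates.

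Two further replies carry some weight. Section 4.1 does not present its list of questions as exhaustive, so a case report form may ask about losses. How past cases are reported and grouped could also be left to an analysis plan. But the protocol names neither item, and an analysis plan can only use what has been collected.

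The cross-sectional reply does not cover incidence, which section 1 claims. Nor does it cover the correlation, where a past case filed as unaffected is misclassified however prevalence is defined. The plan also already looks back: section 4.3 counts bone change since the superstructure was fitted but leaves out its end stage, loss of the implant.

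**Conclusion.** The point holds for incidence, for any ever-affected proportion, and for the make-up of the unaffected group in the tolerance correlation. It does not hold for current prevalence among implants in place.

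The size cannot be derived from the documents. With 20% ever affected and 10 to 25% of these having lost the implant, the shortfall against ever-affected is 1.6 to 4.2 points (ineligible) or at most 2 to 5 points (all enter as healthy). All of these lie inside the 5.5-point half-width, but a systematic shortfall adds to sampling error and does not shrink with more patients. Cases that were treated and resolved would widen the gap; they are not in the figures. Dilution of the tolerance contrast depends on the unproven premise that intolerance contributes to loss, and is modest under these inputs. The change is worth making because the missing data cannot be recovered by analysis and cost little to collect.

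**What to change.** **Section 4.1.** For each enrolled patient, record from the recall chart:

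- the number of implants placed since 1 April 2001;
- the number lost or removed, with date and reason (unknown allowed);
- any earlier treatment of peri-implantitis.

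**Section 5.**

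- Define prevalence as current disease among implants in place.
- Report current-or-past disease beside it.
- Do not claim incidence from the single examination alone. Either drop the term from section 1 or redefine it on the chart data.
- In the correlations, do not count patients with a biological implant loss or treated peri-implantitis as unaffected. Where the reason for loss is unknown, run the correlation both ways.

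**Cost.** A few chart items per patient, with no new visit or procedure. Section 2 says the implants were placed in the participating centres and the patients followed in recall, so the charts should be at hand. The weakness is that reasons for loss will be incomplete.

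A count per centre of recall patients with no implant left would show how many were ineligible. It means searching the charts of non-participants, while section 2 describes consent only for study subjects, so it should be optional.

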#### 4. Course of studies

##### 4.1 General medical history

As part of the survey of the general anamnesis, the underlying internal diseases of all patients are recorded. In particular, questions are asked whether the patient has diabetes mellitus, whether bisphosphonates or acetylsalicylic acid are regularly taken and whether there are allergies. In addition, the patients' smoking habits are asked about.

##### 4.2 Clinical investigation parameters

For patients with multiple implants, a maximum of two implants are examined, the most clinically noticeable and one normal implant. All measurements are carried out by a previously calibrated person using a PCP 12 periodontal probe (Hu-Friedy kal, Germany).

The following clinical parameters are determined:

##### Plaque Index (according to O'Leary):

Determination in each case on the gingival margin to record the cleaning success in 6 places around the implant (mesio-facial, mid-facial, disto-facial, mesio-oral, mid-oral, disto-oral). There is no staining test.

##### Bleeding on probing (BOP):

Determination 30 seconds after probing at 6 points around the implant (mesio-facial, mid-facial, disto-facial, mesio-oral, mid-oral, disto-oral) to determine the peri-implant inflammation status.

##### Probing depths (ST):

measured at 6 places around the implant as a distance: marginal mucosal edge - pocket floor (mesio-facial, mid-facial, disto-facial, mesio-oral, mid-oral, disto-oral).

#### 4.3 X-ray diagnostics

An x-ray image, preferably a dental film, is made for all patients as part of a routine diagnosis. In individual cases, an orthopantomogram can also be made. These are compared with the X-ray images already available at the time the prosthetic superstructure was incorporated and an assessment of the peri-implant bone is carried out.

